1.3.2. Overview of Risks

Use of personal lubricants for anal intercourse is common among both men and women.³⁰ HEC gel has been used extensively in both vaginal^{3,5,31} and, more recently, rectal microbicide studies.

As with all topical formulations, there is the possibility of allergies or sensitivities to the components in the study products (i.e., HEC gel, Key-E®, and Zetpil®). Both Key-E®, and Zetpil® can be administered more than once daily and there are no restrictions to sexual activity noted from the manufacturer. Additionally, a search of available literature found no published information regarding increased risk of side effects from using these products, either as indicated or during intercourse. Those study volunteers with known allergies to similar products or a history of irritation, inflammation, or other signs of sensitivity from similar products or ingredients will be excluded from the study.

All study products will be applied into the rectum (or vagina) using either the HTI Comfort Tip® applicator (gel) or via digital insertion (suppositories). Applicators have accounted for minor epithelial disruptions in vaginal microbicide trials, typically characterized as similar to speculum-related disruptions. For HEC gel, participants will be instructed to use a small amount of the study product to lubricate the applicator prior to insertion. Instructions for suppository use include a wait time of 15 minutes between product insertion and RAI/VI (see Appendix).

Staff will verbally review use of the applicator, showing each step using an empty demonstration applicator. At each product provision visit (V2-4) staff will instruct participants on appropriate insertion

of the assigned product. As part of this process, they will point out the detailed step-by-step instructions in written form. Participants will be given detailed written and illustrated instructions with each product to take home with them. This procedure has worked successfully in our previous vaginal and rectal product evaluation studies.

1.3.3 Pharmacy

All study products will be stored at the Miriam Hospital Pharmacy and dispensed following the receipt of a written prescription from the study clinician. The written prescription will be stored, as per regulatory guidelines, in the research pharmacy's study binder. The site pharmacist is required to maintain complete records of all study products received and subsequently dispensed. HEC will be destroyed per hospital policy after the study is completed or terminated. The two OTC products (Key-E® and Zetpil®) may be transferred to separate storage in [name] lab, to be used for staff training and demonstration purposes only. The procedures to be followed are provided in *Requirements for Pharmacy Activities at DAIDS Supported Clinical Research Sites Conducting Trials Outside of the HIV/AIDS Clinical Trials Networks*.

2. Objectives

2.1 Primary Objectives

- 1) Adapt existing USPE items for evaluation of suppository-associated user sensory perceptions and experiences within the context of rectal or dual compartment use, and
- 2) Using 2 distinct suppository formulations and 1 gel formulation that represent a range of rheological and other biophysical properties of potential microbicides being designed for rectal/dual compartment use, evaluate the experience of suppository use (as compared to gel use) in the context of receptive anal intercourse among males and females, and, for females, in the context of vaginal intercourse.

2.1.1 Primary Endpoints

[figure not shown]
- (1) Generate adapted and novel rectal USPE items to be used in evaluating the perceptibility, user experience and acceptability of rectal and dual compartment topical formulations. Items will be generated from qualitative interview data, thus narrative data (in the form of direct single-source quotes or aggregated quotes across participants with similar sensory and behavioral experiences) will be used to generate statements for subsequent scale items.
- (2) Characterize USPEs of gel and suppository formulations used for RAI and VI using both existing and novel USPE items/scales. Averaged scale item scores for each USPE scale (5 application/insertion scales; 6 ambulation scales; 14 sexual activity scales) will be psychometrically evaluated and, further, will be used to conduct pair-wise comparisons and calculate the effect sizes associated with these comparisons (see section 8).

2.1.2 Exploratory Endpoints

- (3) Collect participant-reported information regarding the safety of the suppository forms. The information collected will include any adverse events (and their severity grading) deemed to be related to the dosage form by the study clinical staff and/or in consultation with the DAIDS Medical Officer. Frequency of specific related adverse events (and their severity) will be calculated cumulatively.

(4) Identify formulation-specific classes of USPE scale scores (Sex-associated scales): by sex (males, females), by compartment (Rectum: males and females. Vagina: females), resulting from Latent Class modeling analyses, given adequate final evaluable sample sizes.

3. Study Design

Visits occur at study clinic (V1) or behavioral lab (V2-V5). Product evaluation activities (RAI (receptive anal intercourse); VI (vaginal intercourse)) represented by triangles occur outside the clinic (e.g., participant's home). ALL participants complete study product evaluations with RAI. FEMALE participants also complete study product evaluations with VI.

This study is a single-site pre-Phase 1 USPE measure development study, utilizing a formative mixed-method design (i.e., incorporating qualitative and quantitative data collection methods). Approximately 20-30 participants (~10-15 males and ~10-15 females) will evaluate three products (Key-E®, Zetpil®, and HEC gel), on separate occasions, during RAI. In addition, female participants will evaluate the suppository products during vaginal sex. Participants will be assigned to one of six possible product orders.

Female participants are not required to have RAI and VI in the same sexual episode, or in different sexual episodes: we will allow them to choose, so that we can begin to understand how sexual sequencing may/may not play a role in product use for women. All participants will be instructed verbally and in writing to limit suppository use to a total of 2 per day, for the women, regardless of rectal or vaginal use.

Participant recruitment, enrollment, and visit completions will require approximately 9-12 months. Analyses (both quantitative and qualitative) will be complete within 24 months from study initiation. Results, in the form of USPE scale scores, by product, sex, and compartment, will be computed. Preliminary psychometric analyses of scales will be completed, given adequate evaluable sample size.

It is estimated that the time from initial prescreen through completion of the final visit for each participant will take, on average, 10-20 weeks. The maximum allowable time from STI/HIV/pregnancy screening to enrollment in the formulation evaluation study is 30 days. If more than 30 days pass and the participant still wishes to enroll in the study, s/he will be required to repeat the screening visit (V1). It is estimated that the prescreen (Visit 0), including, if eligible, collection of contact information, will take 15-25 minutes. Visits 1 and 2, including separate consenting processes, will take approximately 1-1.5 hours; Visits 3 and 4 will take <30 minutes; Visit 5, including the in-depth interview, will take approximately 1.5-2 hours. Daily phone check-ins will be brief (~3 minutes). Web-based USPE surveys will take approximately 45-90 minutes. As per our previous experience in Project DRUM, the average time between product provision visits is expected to be ~2 weeks. (See Appendix for Table of Visits and Study Activities)

4. Study Population

4.1 Selection of the Study Population

The study sample will consist of approximately 20-30 participants (~10-15 males and ~10-15 females) who engage in receptive anal intercourse (RAI; females must also engage in vaginal-penile intercourse,

(VI)). Based on samples previously recruited by this research team, the sample will likely consist of approximately 60-70% White/Caucasian and 30-40% non-White (e.g., Black/African American, Latina/Hispanic, American Indian/Alaska Native) individuals. As calculated from all volunteers who prescreened for Project DRUM and reported at least 1 RAI episode, females reported RAI an average of 14 times in the previous 6 months, with a range of 3-72; males reported RAI an average of 21 times in the previous 6 months, with a range of 4-50. As such, we are confident we will be able to recruit the volunteers necessary to meet the criteria below.

4.2 Inclusion Criteria

All participants must meet all of the inclusion criteria to participate in this study.

- Eligible male participants must be 18 years of age or older
- Eligible female participants must be 18-45 years of age
- Report receptive anal intercourse (RAI) at least twice in the past 6 months,
- Are willing to use each study product in conjunction with RAI on at least one occasion in each data collection period (resulting in a minimum of 3 RAI events during the study)
- Are willing and able to respond to study data collection systems via phone and internet, attend all study visits, and participate in in-depth qualitative interviews

Additional Inclusion Criteria for Female Volunteers:

- report vaginal-penile intercourse (VI) at least twice in the past 6 months,
- willing to use each study suppository formulation in conjunction with VI on at least one occasion in each data collection period (resulting in a minimum of 2 vaginal intercourse events during the course of the study)
- report consistent use of an effective birth control method: e.g., hormonal contraceptive, IUD, bilateral tubal ligation, Essure® or any non-incisional permanent birth control procedure, hysterectomy (partial or total, with/without oophorectomy), partner's vasectomy/salpingectomy

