Study Design	Single-site, pre-phase 1, mixed methods USPE instrument development study
Study Population	Healthy, HIV uninfected participants, male ≥ 18 years of age and female 18-45 years of age. By history receptive anal intercourse (RAI) at least twice in the past 6 months and women in addition vaginal-penile intercourse (VI) at least twice in the past 6 months.
Sample Size	Approximately 20-30 participants (~10-15 males; ~10-15 females). Our goal is to recruit a minimum of ~7-10 males and ~7-10 females. Ranges are provided to allow for a gender imbalance in the sample if we experience difficulty with recruitment, and to allow for achieving data saturation in qualitative data collection.
Study Contacts	
Visit 0: Pre-screening (by phone or in person) to confirm basic eligibility
 
Visit 1: Informed consent (Screening), STI/HIV screening; pregnancy screening (females); CASI Clinic Survey
 
Visit 2: Pregnancy screening (females), informed consent (Formulation Evaluation), random assignment to order of study products, provision of 1st study product, CASI Baseline Survey
 
Visits 3-4: Pregnancy screening (females), provision of 2nd and 3rd study products, respectively
 
Visit 5: In-depth qualitative interview (IDI) with survey evaluation (cognitive) elements
 
Visit 2-Visit 5: Automated daily phone check-ins Web-based USPE surveys completed following each occurrence of RAI/VI in conjunction with study product use. Final product acceptability survey completed after the final USPE survey. Compensation for all study activities completed since the previous visit (daily phone check-ins, web-based surveys) and not yet compensated, will occur with each study visit

Study Duration	
Study duration: Participant recruitment, enrollment, visit completions: 9-12 months. Analyses: within 24 months from start of study.
 
Per participant: Approximately 10-20 weeks. We do not anticipate the necessity of additional time beyond the range allotted for female participants to evaluate suppositories in both compartments (§3).

Study Regimen/ Intervention	
Products :
 
 -- HEC gel (CONRAD, Arlington, VA) – applicator insertion -- Key-E suppository –manual insertion -- Zetpil suppository – manual insertion

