4.3 Exclusion Criteria

All potential participants meeting any of the exclusion criteria at screening or study visits will be excluded from study participation. Male and female participants will be ineligible if they:

- Have a sensitivity or allergy to vaginal, anal, or rectal products,
- Have a sensitivity or allergy to any of the ingredients contained in the study products
- Have a sensitivity or allergy to sesame seeds
- Are HIV-positive at baseline, or have a known HIV-positive sexual partner,
- Have an active rectal or reproductive tract infection requiring treatment per current CDC guidelines or have other condition that, in the opinion of the investigator/study clinician, make the patient unsuitable for the study or unable to comply with study requirements (Note: HSV seropositivity without active genital lesions is not an exclusion criteria).
- Urinary tract infection (UTI).
- Have current inflammatory bowel disease (IBD) or history of active IBD within last 3 months,
- Have any other significant colorectal symptom(s) as determined by medical history, participant self-report, or physical exam (including but not limited to presence of any unresolved injury, infectious or inflammatory condition of the local mucosa, presence of symptomatic external hemorrhoids, and presence of any painful anorectal conditions that would be tender to manipulation),

- Have any other clinical condition or prior therapy that, in the opinion of the investigator/study clinician, would make the patient unsuitable for the study or unable to comply with the study requirements (including, as determined by medical history, participant self-report, or physical exam),
- Are unwilling to refrain from use of nonoxynol-9 (N9) for the duration of the study
- Are currently enrolled in other rectal or vaginal product studies
- Are unable or unwilling to communicate in English, or
- Are unable or unwilling to give written informed consent

Additional Exclusion Criteria for Female Volunteers:

- Are pregnant or breastfeeding. Pregnancy testing will be conducted at Visits 1-4 (screening and prior to any product use period)
- Have completed menopause (i.e., at least 12 months without menstrual periods)
- Are currently attempting to get pregnant or have an intention to get pregnant during their participation in the study
- Are unwilling to refrain from use of any vaginal product (inclusive of douching; exclusive of tampons during menses) other than study products

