8.3.3 Statistical Considerations

Given the planned sample size (n~20-30), and the formative nature of this research, statistical comparisons between products are not the most important aim of this study. However, assuming the larger sample size (i.e., 24-30, 12-15 males and 12-15 females) is achieved and conditions for USPE scale comparisons are met (i.e., analyses indicate good psychometric properties of existing scales, such that we confirm each scale's internal validity by verifying high item scale loadings and we find good internal consistency for a specific scale as measured by the Coefficient Alpha statistic), we will compare products and compute the effect sizes for all of the comparisons of each formulation between sexes (i.e., given 12-15 males and 12-15 females), between compartments (females), and between formulations to provide guidance for outcomes interpretation and for future studies. While we do not expect all comparisons between products to be statistically significant as the relatively small sample size places limits on statistical power, we do anticipate that some comparisons may be statistically significant based on our past research into scale score comparisons conducted on a number of different products. For example, with respect to sexual activity scales in our previous study among a sample of 24 heterosexual couples using vaginal formulations and engaging in vaginal-penile sex, effect sizes resulting in significant differences in pair-wise comparisons of 3 different formulation conditions ranged from 0.60 (considered a medium effect size) to 2.67 (considered a very large effect size). In Project DRUM (section 1.1a), among a sample of 15 (8 male; 7 female) participants using rectal formulations and engaging in receptive anal intercourse, effect sizes ranged from small to medium.

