We will first provide an overall description of the sample of participants using means, standard deviations and percentages, as appropriate, to examine demographic variables such as age, sex, and race/ethnicity, as well as sexual/reproductive history variables. After conducting the psychometric analyses, we will also calculate scale scores associated with the USPE scales being evaluated and compare them as noted in 2.1.1(2) above. These scores will be considered in relation to the biophysical measures associated with the formulations being evaluated. Specifically, we will quantitatively examine responses on the pre-existing and adapted/new user perception scales, within both females and males, for perceptual differences between products on the different scales using paired t-tests. Given our small sample size and the new context of the study parameters, we will not apply a correction for the number of statistical tests conducted, to guard against Type II statistical errors. We will also calculate effect sizes for each product comparison as a Cohen's d statistic.³⁴ Secondary analyses that examine group differences (e.g., age, race/ethnicity, etc) across behavioral dimensions and formulation ratings will also be conducted, using independent t-tests, analysis of variance, and Pearson correlations, as appropriate, and as data allows. Further, other quantitative data may be used (e.g., USPE scale scores and their statistics; willingness-to-use; pairwise comparisons) to stratify participants in the qualitative data to determine whether themes and patterns vary as a function of those variables.

9. Data Handling and Record Keeping

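### Men have no upper age limit and women stop at 45, so the planned between-sex effect sizes are at risk of confounding by age and should also be shown over the shared 18-45 range

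*Combined protocol and SAP*

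**What the plan says.** Section 4.2 gives different age limits by sex: "Eligible male participants must be 18 years of age or older" and "Eligible female participants must be 18-45 years of age". The Protocol Summary repeats them ("male ≥ 18 years of age and female 18-45 years of age"), so this is not a slip in one section. Section 4.3 also excludes women who have completed menopause.

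Section 8.3.3 plans to "compute the effect sizes for all of the comparisons of each formulation between sexes". This is conditional, "assuming the larger sample size (i.e., 24-30, 12-15 males and 12-15 females) is achieved", and the scales must also show good psychometric properties.

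Age is collected. Section 8.4.2 describes the sample on "demographic variables such as age, sex, and race/ethnicity" and lists secondary analyses of ratings by age and other characteristics, using t-tests, analysis of variance and correlations. Section 1.2 allows demographic data to serve as strata or covariates in possible analyses, but names neither age nor the sex contrast. Section 8.3.2 seeks participants who vary in age and has no provision for balancing age between the sexes.

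**The concern.** Over 45 there can be men in the sample but no women. An unadjusted between-sex effect size therefore compares groups whose permitted age ranges differ, and the plan offers no view of that contrast over the range they share.

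Examining age separately, as Section 8.4.2 does, does not take age out of the sex contrast. It also has the mirror problem: in a pooled analysis, a difference between older and younger participants may be a difference between men and women.

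What is at stake is interpretation. Section 1.1.2 reads sex differences in the preceding DRUM study as a sign that men and women may report their experience differently. Section 8.3.3 wants the effect sizes as guidance for future studies, and Section 6.5.2 says the data will enter later validation analyses. Pooling reduces sampling error but would not remove a systematic age component.

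**Working it through.** The documents give no age distribution, age-score correlation, significance level or target between-sex effect. There is no stated figure to reproduce, and what follows is an illustration.

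**From the documents:** women 18-45; men 18 and over; 12 to 15 per sex for the contrast.

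**Assumed:** ages uniform within each sex; men up to 55, 65 or 75; within-sex age-score correlation ρ of 0.1 to 0.5; linear age effect; two-sided 5% level.

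**1. Age gap.** A uniform range from a to b has mean (a+b)/2 and variance (b−a)²/12.
- Women 18-45: mean 31.5, variance 27²/12 = 60.75.
- Men 18-55: mean 36.5, variance 37²/12 = 114.08. The gap is 5 years, the pooled SD is √[(60.75+114.08)/2] = 9.35, and the standardised gap is 0.53.
- Men 18-65: mean 41.5, variance 47²/12 = 184.08. The gap is 10 years, the pooled SD is 11.06, and the standardised gap is 0.90.
- Men 18-75: the gap is 15 years and the standardised gap is 1.17.

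**2. Bias in the unadjusted between-sex Cohen's d** = ρ × standardised gap.

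| Men up to | ρ = 0.1 | ρ = 0.3 | ρ = 0.5 |
|---|---|---|---|
| 45 | 0 | 0 | 0 |
| 55 | 0.05 | 0.16 | 0.27 |
| 65 | 0.09 | 0.27 | 0.45 |
| 75 | 0.12 | 0.35 | 0.58 |

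At ρ = 0 the bias is zero whatever the ages. Its direction follows the sign of ρ.

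**3. Sampling error.** The standard error of d near zero is about √(2/n): 0.41 at 12 per sex and 0.37 at 15. The smallest d significant at 5% is 0.85 and 0.75 respectively. The 0.16 to 0.27 case is below one standard error.

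**4. Simulation** (6,000 runs per setting, no true sex effect, men 18-65, ρ = 0.3). The unadjusted contrast was biased by 0.26 to 0.28 SD and rejected in 9.2% of runs at 12 per sex and 11.5% at 15. With age as a linear covariate the bias was about zero and rejection was 4.9% and 5.2%. When age acted only above 45, linear adjustment left about 0.06 SD of bias.

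**5. Cost of each remedy.**
- *Covariate.* With men 18-65, the squared correlation of sex with age is 25/(122.42+25) = 0.17. Variance inflation is 1/(1−0.17) ≈ 1.2, so the standard error rises by about 10%. One further degree of freedom is used, of 22 to 28.
- *Restriction to 18-45.* The share of men over 45 is 10/37 = 27% (men to 55) or 20/47 = 43% (men to 65). Of 12 to 15 men, about 7 to 11 remain. With 7 men and 12 women the standard error is √(1/7+1/12) = 0.48, against 0.41 unrestricted.

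**The case against.** A reader might infer from the eligibility rules that every between-sex contrast in this study is confounded by age. The documents do not support that. Confounding needs a real age gap among those enrolled and a real association of age with score, and the documents supply neither. An open upper limit permits an imbalance but does not create one.

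It is also tempting to set the assumed bias against the small-to-medium effects quoted from DRUM in Section 8.3.3. Section 1.1.2 shows that the small-to-medium range describes differences between gels in the whole sample, and it reports larger differences within and between the sexes. That benchmark is not used here.

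The other arguments have weight. The contrast is conditional and descriptive, in a study that says standard hypothesis testing is not an appropriate endpoint. The product comparisons in Section 8.4.2 are paired within person, and the compartment comparison is made within women, so a between-sex age gap does not confound either. Section 1.2 already permits covariates. The two cohorts differ in other ways too: Section 4.1 reports a mean of 21 episodes of receptive anal intercourse in six months for men and 14 for women among DRUM prescreeners, and only women have vaginal intercourse and contraception criteria. Handling age would not isolate sex.

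All of this limits the point without removing it. Permission to use covariates is not a plan to use one here, and age is the characteristic on which eligibility itself leaves part of one group with no counterpart.

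**Conclusion.** The point holds as a risk confined to the between-sex effect sizes. The age limits differ by sex, the contrast is planned, age is collected, and nothing links age to that contrast. Whether bias arises, and how much, cannot be known from the documents. About 0.16 to 0.27 SD is an illustration resting on uniform ages, men up to 55 or 65 and a correlation of 0.3. It would be hard to see within this study's own sampling error, and it vanishes if the enrolled ages match or age does not matter.

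The illustration might suggest making the age-adjusted estimate the main one. That goes too far: above 45 the model has no women to compare, so it extrapolates on an assumed straight line with 12 to 15 per sex. Neither primary endpoint depends on the contrast. Severity is minor, and this is a cheap improvement.

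**What to change.** In Section 8.4.2:

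- Report the age distribution by sex, including the number of men over 45.
- Beside each between-sex effect size, show the same effect size restricted to participants aged 18-45, with its confidence interval.
- As a supporting analysis, show the contrast with age as a linear covariate, and state the linearity assumption.
- Describe a sex difference that does not persist as not separable from age. Judge persistence by the effect sizes and their intervals, because significance may be lost through smaller numbers alone. Describe one that does persist as a difference between the two cohorts as recruited.

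Enrolment, visits and data collection do not change. The restricted contrast may hold fewer than the 12 men that Section 8.3.3 requires, so the plan should say that it is shown regardless, as a sensitivity analysis. The adjusted contrast costs one degree of freedom and, in the illustration with men up to 65, about a 1.2-fold increase in variance. If few men over 45 enrol, the restricted and full results will nearly coincide and the age table alone will largely settle the matter.
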